8.3.4.2. Local Reactions

During the reactogenicity e-diary reporting period, participants will be asked to assess redness, swelling, and pain at the injection site and to record the symptoms in the reactogenicity e-diary.

If a local reaction persists beyond the end of the reactogenicity e-diary period following vaccination, the investigator will enter this information into the CRF and follow up at the next study visit to obtain stop dates for local reactions that have resolved.

Participants will be provided with a measuring device. Redness and swelling will be measured and recorded in measuring device units (range: 1 to 21) and then categorized during analysis as absent, mild, moderate, or severe based on the grading scale in Table 1. Measuring device units can be converted to centimeters according to the following formula: 1 measuring device unit = 0.5 cm. Pain at the injection site will be assessed by the participant as absent, mild, moderate, or severe according to the grading scale in Table 1.

If a Grade 3 local reaction is reported in the reactogenicity e-diary, a telephone contact should occur to ascertain further details and determine whether a site visit is clinically indicated. Only an investigator or medically qualified person can classify a participant's local reaction as Grade 4. If a participant experiences a confirmed Grade 4 local reaction, the investigator must immediately notify the sponsor and, if it is determined to be related to the administration of the study intervention, further vaccinations will be discontinued in that participant.

		•		
	Mild Grade 1	Moderate Grade 2	Severe Grade 3	Grade 4ª
Pain at the injection site	Does not interfere with activity	Interferes with activity	Prevents daily activity	Emergency room visit or hospitalization for severe pain
Redness	>2.0 cm to 5.0 cm (5 to 10 measuring device units)	>5.0 cm to 10.0 cm (11 to 20 measuring device units)	>10 cm (≥21 measuring device units)	Necrosis or exfoliative dermatitis
Swelling	>2.0 cm to 5.0 cm (5 to 10 measuring	>5.0 cm to 10.0 cm (11 to 20 measuring	>10 cm (≥21 measuring	Necrosis

Table 1. Local Reaction Grading Scale

device units)

device units)

device units)

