8.3.4.3. Systemic Events

During the reactogenicity e-diary reporting period, participants will be asked to assess vomiting, nausea, diarrhea, headache, fatigue, chills, new or worsened muscle pain, and new or worsened joint pain and to record the symptoms in the reactogenicity e-diary. The symptoms will be assessed by the participant as absent, mild, moderate, or severe according to the grading scale in Table 2.

If a systemic event persists beyond the end of the reactogenicity e-diary period following vaccination, the investigator will enter this information into the CRF and follow up at the next study visit to obtain stop dates for the events that have resolved.

If a Grade 3 systemic event is reported in the reactogenicity e-diary, a telephone contact should occur to ascertain further details and determine whether a site visit is clinically indicated. Only an investigator or medically qualified person can classify a participant's systemic event as Grade 4. If a participant experiences a confirmed Grade 4 systemic event, the investigator must immediately notify the sponsor and, if it is determined to be related to the administration of the study intervention, further vaccinations will be discontinued in that participant.

Table 2. Systemic Event Grading Scale

	Mild Grade 1	Moderate Grade 2	Severe Grade 3	Grade 4ª
Fatigue (= tiredness)	Does not interfere with activity	Some interference with activity	Prevents daily routine activity	Emergency room visit or hospitalization for severe fatigue
Headache	Does not interfere with activity	Some interference with activity	Prevents daily routine activity	Emergency room visit or hospitalization for severe headache

a. Only an investigator or qualified designee can classify a participant's local reaction as Grade 4, after clinical evaluation of the participant or documentation from another medically qualified source (eg, emergency room or hospital record) or contact with the participant. Grade 4 local reactions will be collected on the AE CRF and assessed by the investigator using the AE intensity grading scale as detailed in Section 10.3.3.

Table 2. Systemic Event Grading Scale
Mild Modera

	Mild Grade 1	Moderate Grade 2	Severe Grade 3	Grade 4ª
Vomiting	1 to 2 times in 24 hours	>2 times in 24 hours	Requires intravenous hydration	Emergency room visit or hospitalization for severe vomiting

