8.3.4.4. Fever Monitoring

To record information on fever, a thermometer will be given to participants with instructions on how to measure oral temperature at home. Temperature will be collected in the reactogenicity e-diary in the evening daily during the 7-day reactogenicity e-diary reporting periods. It will also be collected at any time during the reactogenicity e-diary data collection periods when fever is suspected. Fever is defined as an oral temperature of ≥38.0°C (≥100.4°F). The highest temperature for each day will be recorded in the e-diary, where possible. Temperature will be measured and recorded to 1 decimal place. Temperatures recorded in degrees Fahrenheit will be programmatically converted to degrees Celsius and then categorized according to the ranges shown in Table 3 during analysis.

If a fever of ≥39.0°C (≥102.1°F) is reported in the e-diary, a telephone contact with the participant should occur to ascertain further details and determine whether a site visit is clinically indicated. Only an investigator or medically qualified person can confirm a participant's fever as >40.0°C (>104.0°F). If a participant experiences a confirmed fever >40.0°C (>104.0°F), the investigator must immediately notify the sponsor. Grade 4 fevers will be collected on the AE CRF and assessed by the investigator using the AE intensity grading scale as detailed in Section 10.3.3.

Table 3. Ranges for Fever

Mild Grade 1	Moderate Grade 2	Severe Grade 3	Grade 4ª
	>38.4°C to 38.9°C	>38.9°C to 40.0°C	>40.0°C
(100.4-101.1°F)	(101.2-102.0°F)	(102.1-104.0°F)	(>104.0°F)

a. Only an investigator or qualified designee can classify a participant's fever as Grade 4, after clinical evaluation of the participant, documentation from another medically qualified source (eg, emergency room or hospital record), or contact with the participant. Grade 4 fevers will be collected on the AE CRF and assessed by the investigator using the AE intensity grading scale as detailed in Section 10.3.3.

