 related to the event.
- The investigator will then record all relevant AE or SAE information in the CRF.
- It is not acceptable for the investigator to send photocopies of the participant's medical records to Pfizer Safety in lieu of completion of the Vaccine SAE Reporting Form/AE or SAE CRF page.
- There may be instances when copies of medical records for certain cases are requested by Pfizer Safety. In this case, all participant identifiers, with the exception of the participant number, will be redacted on the copies of the medical records before submission to Pfizer Safety.
- The investigator will attempt to establish a diagnosis of the event based on signs, symptoms, and/or other clinical information. Whenever possible, the diagnosis (not the individual signs/symptoms) will be documented as the AE or SAE.

Assessment of Intensity

The investigator will make an assessment of intensity for each AE and SAE reported during the study and assign it to 1 of the following categories:

GRADE	If required on the AE page of the CRF, the investigator will use the adjectives MILD, MODERATE, SEVERE, or LIFE-THREATENING to describe the maximum intensity of the AE. For purposes of consistency, these intensity grades are defined as follows:					
1	MILD	LD Does not interfere with participant's usual function.				
2	MODERATE	Interferes to some extent with participant's usual function.				
3	SEVERE	Interferes significantly with participant's usual function.				
4	LIFE-THREATENING	Life-threatening consequences; urgent intervention indicated.				

An event is defined as "serious" when it meets at least 1 of the predefined outcomes as described in the definition of an SAE, NOT when it is rated as severe.

Assessment of Causality

- The investigator is obligated to assess the relationship between study intervention and each occurrence of each AE or SAE. The investigator will use clinical judgment to determine the relationship.
- A "reasonable possibility" of a relationship conveys that there are facts, evidence, and/or arguments to suggest a causal relationship, rather than a relationship cannot be ruled out.
- Alternative causes, such as underlying disease(s), concomitant therapy, and other risk factors, as well as the temporal relationship of the event to study intervention administration, will be considered and investigated.
- The investigator will also consult the IB and/or product information, for marketed products, in their assessment.

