- For pain at the injection site and all other systemic events, the severity grading algorithm for the e-diary data and the AE CRF may not be the same, though Pfizer will choose the highest-severity grade.

If a participant did not have any e-diary data transferred, the AE CRF data will not be used for derivation because the analysis of reactogenicity will be based on e-diary safety population, which is only restricted to participants who have at least 1 day of e-diary data entered. In other words, if a participant did not report any e-diary data, the participant will not be included in the analysis of reactogenicity data.

Safety	Vaccine Group (as Received)				
Endpoints	Combination:	Sequential	qIRV Alone	RSVpreF	Placebo Only
	RSVpreF +	Administration:		Alone	
	qIRV	qIRV/RSVpreF			
Local	Local reactions	Local reactions	Local reactions	Local reactions	Local reactions
reactions	reported within	reported within	reported within	reported within	reported within
within	7 days after	7 days after	7 days after	7 days after	7 days after
7 days after	Vaccination 1	Vaccination 1 or	Vaccination 1	Vaccination 2	Vaccination 2
vaccination	among	after Vaccination 2	among	among	among
	participants who	among participants	participants who	participants who	participants who
	received the	who received qIRV	received qIRV at	received	received placebo
	combination	at Visit A101 with	Visit A101 with	RSVpreF at	only at Visit
	vaccine at	at least 1 day of	at least 1 day of	Visit A102 with	A102 with at
	Visit A101 with	e-diary transferred	e-diary data	at least 1 day of	least 1 day of
	at least 1 day of	following the	transferred	e-diary data	e-diary data
	e-diary data	vaccination and	following the	transferred	transferred
	transferred	received RSVpreF	vaccination.	following the	following the
	following the	at Visit A102 with		vaccination.	vaccination.
	vaccination.	at least 1 day of			
		e-diary data			
		transferred			
		following the			
		vaccination.			

The table below lists safety endpoints that will be derived for each vaccine group.

DMB02-GSOP-RF02 7.0 Statistical Analysis Plan Template 31-Jan-2022 PFIZER CONFIDENTIAL TMF Doc ID: 98.03 Page 18 of 46

Safety	Vaccine Group (as Received)				
Endpoints	Combination: RSVpreF + qIRV	Sequential Administration: qIRV/RSVpreF	qIRV Alone	RSVpreF Alone	Placebo Only

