3.1.3.1.2. Maximum Severity of Local Reactions Within 7 Days After Vaccination

The grading of local reactions is listed in Table 5.

 Table 5.
 Grading Scale for Local Reactions

	Mild Grade 1	Moderate Grade 2	Severe Grade 3 ^a	Grade 4 ^b
Redness	2.5 cm to 5.0 cm	>5.0 cm to 10.0 cm	>10 cm	Necrosis or exfoliative
	(5 to 10 measuring	(11 to 20 measuring	(>20 measuring	dermatitis
	device units from	device units from the	device units from	
	the e-diary) or mild	e-diary) or moderate	the e-diary) or	
	from the AE CRF.	from the AE CRF.	severe from the AE	
			CRF.	

DMB02-GSOP-RF02 7.0 Statistical Analysis Plan Template 31-Jan-2022 PFIZER CONFIDENTIAL TMF Doc ID: 98.03 Page 20 of 46

	Mild	Moderate	Severe	Grade 4 ^b
	Grade 1	Grade 2	Grade 3 ^a	
Swelling	2.5 cm to 5.0 cm	>5.0 cm to 10.0 cm	>10 cm	Necrosis
_	(5 to 10 measuring	(11 to 20 measuring	(>20 measuring	
	device units from	device units from the	device units from	
	the e-diary) or mild	e-diary) or moderate	the e-diary) or	
	from the AE CRF.	from the AE CRF.	severe from the AE	
			CRF.	
Pain (at the	Does not interfere	Interferes with	Prevents daily	Emergency room visit or
injection site)	with activity (mild	activity (moderate	activity (severe	hospitalization for severe
	from the e-diary or	from the e-diary or	from the e-diary or	pain at the injection site.
	the AE CRF).	the AE CRF).	the AE CRF).	

 Table 5.
 Grading Scale for Local Reactions

a. The maximum reaction size in measuring device units is 21 (10.5 cm). Any reaction size >21 measuring device units is recorded as a number that is >20 (eg, 21) in the e-diary.

b. Grade 4 assessment should be made by the investigator using the AE severity grading scale. The assessment will be collected on the AE CRF and thus not reported from the e-diary.

The following variables are derived for each participant included in the reactogenicity subset:

1. Maximum severity of each local reaction on any day (Day 1 through Day 7).

The maximum severity (highest grading) of each local reaction within 7 days after vaccination will be derived. The maximum severity will be derived as follows:

= Missing, if values are missing for all days (Day 1 through Day 7).

= 0, if the participant reports all reactions as "no" or a combination of missing and "no" for all days (Day 1 through Day 7).

= *Highest grade* (maximum severity) within 7 days after vaccination, if the answer is not "no" for at least 1 day.

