3.1.3.2. Systemic Events

Systemic events, including fever, fatigue, headache, vomiting, nausea, diarrhea, chills, new or worsened muscle pain, and new or worsened joint pain, are reported from Day 1 through Day 7 after vaccination, where Day 1 is the day of vaccination with combination RSVpreF + qIRV, qIRV, RSVpreF, or placebo. The derivations for the systemic events, for each of the 5 vaccine groups as described below, will be handled similarly to the way local reactions are handled for the presence for each participant, severity level, duration, onset day, and systemic event on each and any day:

- 1. Presence (yes or no) of each systemic event on any day (Day 1 through Day 7) after vaccination.
- 2. Presence (yes or no) of any systemic event on any day (Day 1 through Day 7) after vaccination.
- 3. Maximum severity of each systemic event on any day (Day 1 through Day 7) after vaccination.
- 4. Maximum severity of any systemic event on any day (Day 1 through Day 7) after vaccination.
- 5. Duration of each systemic event after vaccination.
- 6. Onset day of each systemic event after vaccination.
- 7. Presence (yes or no) of each systemic event on each and any of the 7 days after Vaccination.
- 8. Presence (yes or no) of any systemic event on each and any of the 7 days after Vaccination.

The grading scale for systemic events is provided in the protocol. However, the derivation of severity of each systemic event on each day should be based on the maximum severity reported from the e-diary or the AE CRF, if data are reported from both sources; or the e-diary alone if not reported from the AE CRF.

Fever is defined as a temperature of $\geq 100.4^{\circ}$ F ($\geq 38.0^{\circ}$ C). The highest temperature for each day will be recorded in the e-diary. For reporting purposes, fever will be analyzed using the following temperature ranges:

- Mild (\geq 38.0 to 38.4°C from the e-diary or mild grade from the AE CRF).
- Moderate (>38.4 to 38.9°C from the e-diary or moderate grade from the AE CRF).
- Severe (>38.9 to 40.0°C from the e-diary or severe grade from the AE CRF).
- Grade 4 (>40.0°C from the e-diary or severe grade from the AE CRF plus documented >40.0°C in CRF query or other sources).

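### A confirmed Grade 4 local reaction or systemic event that is not life-threatening would be tabulated as Grade 3, because its grade is taken from the AE intensity scale

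*SAP*

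**What the plan says.** **Criterion.** Protocol 8.3.4.2 (Table 1) sets Grade 4 injection-site pain at "Emergency room visit or hospitalization for severe pain". Grade 4 redness is necrosis or exfoliative dermatitis, and Grade 4 swelling is necrosis. Protocol 8.3.4.3 (Table 2) uses the same pattern for systemic events, for example "Emergency room visit or hospitalization for severe headache". SAP Table 5 repeats the local criteria in its Grade 4 column.

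**Scale.** Footnote a to each of Protocol Tables 1, 2 and 3 sends Grade 4 events to the AE CRF, where the investigator rates them on the intensity scale of Protocol 10.3.3. On that scale Grade 3 is severe and Grade 4 is "Life-threatening consequences; urgent intervention indicated". SAP Table 5 footnote b follows suit: "Grade 4 assessment should be made by the investigator using the AE severity grading scale". It adds: "The assessment will be collected on the AE CRF and thus not reported from the e-diary".

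**Derivation.** SAP 3.1.3 names two sources of reactogenicity data, the e-diary and the AE CRF. It accepts that the two may grade pain and systemic events differently, "though Pfizer will choose the highest-severity grade". SAP Table 5 maps a severe rating on the AE CRF to Grade 3. SAP 3.1.3.2 takes the maximum of the two sources for systemic events.

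**Fever.** SAP 3.1.3.2 has its own rule: "Grade 4 (>40.0°C from the e-diary or severe grade from the AE CRF plus documented >40.0°C in CRF query or other sources". Protocol 8.3.4.4 says of a fever above 40.0°C: "Only an investigator or medically qualified person can confirm" it.

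**The concern.** The criterion and the scale describe different things. An emergency room visit for severe pain need not be life-threatening, so an event can meet the Table 1 or 2 definition of Grade 4 and still be rated severe on the AE CRF. The SAP has no rule that takes such a record to Grade 4.

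Maximum severity is part of the primary safety display in both substudies (Protocol Tables 5 and 8; SAP 6.1.3.1 and 6.1.6). Substudy B also aims to choose between two formulations that may differ in injection-site reactogenicity. Misplacement here runs one way: local and systemic events move down from Grade 4 to Grade 3. The protocol also requires the sponsor to be told at once of a confirmed Grade 4 event, so the conduct records and the tables could disagree about the same participant.

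**Working it through.** No figure in the plan depends on this point, so the check is a trace of the rules followed by an illustration of size.

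**Trace.** Take a severe headache that leads to an emergency room visit without admission and is not life-threatening.

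| Step | Source | Grade |
|---|---|---|
| Symptom criterion | Protocol Table 2 | 4 |
| E-diary | Response options end at severe (Protocol 8.3.4.3) | 3 at most |
| AE CRF | Protocol 10.3.3, rated severe | 3 |
| Tabulated | SAP 3.1.3.2, max(3, 3) | 3 |

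If the investigator rates it moderate on the AE CRF, the result is max(3, 2) = 3. Only a life-threatening rating gives max(3, 4) = 4. The same trace applies to injection-site pain, redness and swelling through SAP Table 5, where a severe AE CRF rating is explicitly Grade 3.

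**Contrast with fever.** An AE CRF fever rated severe becomes Grade 4 if a temperature above 40.0°C is documented. That links the AE rating back to the reactogenicity criterion. No other event has such a link.

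**Visibility elsewhere.** SAP 3.1.3.3 and 3.2.1.1 remove AE records classed as reactogenicity from the AE derivations unless they are serious or lead to discontinuation. Inpatient hospitalization is an SAE criterion (Protocol 10.3.2), so admitted cases remain in the SAE summaries. What can lose its label is a non-serious emergency room visit, or non-serious necrosis or exfoliative dermatitis.

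**Size.** The SAP uses Clopper-Pearson intervals. For 0 of n, the upper 95% limit is 1 − 0.025^(1/n). For 1 of n, the lower limit is 1 − 0.975^(1/n) and the upper limit is the 97.5% quantile of Beta(2, n − 1). With planned group sizes, one affected participant changes the Grade 4 row as follows:

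| Group | By Table 1/2 criterion | By AE scale |
|---|---|---|
| Substudy A, n=125 | 1/125 = 0.8% (0.02 to 4.38) | 0% (0 to 2.91) |
| Substudy B, n=100 | 1/100 = 1.0% (0.03 to 5.45) | 0% (0 to 3.62) |
| Substudy B age group, n=50 | 1/50 = 2.0% (0.05 to 10.65) | 0% (0 to 7.11) |

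Actual e-diary denominators may be smaller.

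**Fever in the other direction.** The SAP counts a diary value above 40.0°C as Grade 4 without asking for confirmation. The protocol requires contact at 39.0°C or above, and contact or a visit to confirm a suspected Grade 4. The SAP drops values confirmed as errors (3.1.3, 3.1.3.2). Only a value that is neither confirmed nor refuted is left in question.

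**The case against.** The strongest reply is that the footnotes describe two steps. The investigator first classifies the reaction as Grade 4, then gives that reaction an AE intensity rating, and nothing says the rating cancels the classification. Unscheduled visits are assessed on the reactogenicity scale and have their own CRF, and the clinical team reviews AEs within 7 days of vaccination before database lock. This is a fair reading of the protocol. It does not settle the SAP: the derivation uses only the e-diary and the AE CRF, does not name the unscheduled-visit CRF, and sends a severe AE CRF rating to Grade 3.

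Four stronger readings are tempting, and the documents do not support them.

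- *The SAP departs from the protocol.* It does not. The protocol's own footnotes require the AE scale; the tension starts there and SAP footnote b repeats it.
- *Grade 4 cannot be tabulated, or its row must stay empty.* Life-threatening events reach Grade 4 on either definition.
- *Affected events survive only as Grade 3 reactions.* Not when they are serious or lead to discontinuation; those stay in the AE data.
- *The fever rule is wrong and unconfirmed values should be downgraded.* The protocol itself says diary temperatures are categorized by the Table 3 ranges at analysis, and counting an unresolved high reading is a defensible cautious convention in a safety table.

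It also stands that neither substudy tests a hypothesis, and that solicited reactions within 7 days are excluded from the last stopping criterion's count of Grade 3 or higher AEs.

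**Conclusion.** The point holds as a minor inconsistency. By the SAP's stated rules, a confirmed Grade 4 local reaction or systemic event that is not life-threatening is displayed as Grade 3. The effect is confined to the maximum-severity tables and bar charts; any-severity rates do not change. One affected participant moves the Grade 4 row by 0.8 percentage points in a Substudy A group, 1.0 in a Substudy B group and 2.0 in a Substudy B age group of 50.

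This rests on two assumptions: that the investigator applies the 10.3.3 definitions literally on the AE CRF, and that the unscheduled-visit CRF is not used, since the SAP does not mention it. The documents give no expected rate for such events, so the figures illustrate one event and do not predict a count. The fever discrepancy is smaller still and calls only for the texts to be reconciled.

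**What to change.** Reconcile the footnotes to Protocol Tables 1 and 2 with SAP Table 5 and SAP 3.1.3.2. State in the SAP that the maximum-severity tables assign Grade 4 when the investigator-confirmed record (AE CRF, unscheduled-visit CRF or query) meets the Table 1 or 2 criterion, whatever the AE intensity rating. This is the same kind of link the SAP already gives AE CRF fever.

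For fever, reconcile SAP 3.1.3.2 with Protocol 8.3.4.4 and say how a diary value above 40.0°C that is neither confirmed nor refuted is displayed, for example counted but flagged as unconfirmed. Downgrading it is not needed.

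The cost is wording in both documents plus a derivation rule or a query for a few records. This assumes that the CRF or queries capture non-serious emergency room visits, which cannot be checked because the CRF is not among the documents. If they do not, a query before database lock would be needed for each candidate record.
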